Study Protocol and Statistical Analysis Plan

Title of the study: Nurse-Led Community Health Worker Adherence Model in 3HP Delivery Among Homeless Adults at Risk for TB Infection and HIV (3HP-LTB)

NCT Number: NCT03702049

Document Date: January 2, 2024

Procedures

Recruitment, Informed Consent, and Compensation

A well-trained RN and CHWs visited shelters and informed residents frequenting the sites about the study. Approved flyers were posted, and informational session presentations were given by the staff in the lobbies of the shelters where residents and visiting homeless awaited services. After informed consent was administered, a brief 2-minute structured questionnaire, which assessed TB history, followed. All potentially eligible participants were escorted to our community-based partner clinic in Skid Row and were tested with a blood assay using QuantiFERON-TB Gold Plus, a tuberculin skin test alone, or a combination of screening with the tuberculin skin test followed by the QuantiFERON-TB Gold Plus, as well as other routine testing (i.e., liver function and HIV tests). LTBI-positive homeless adults were escorted back to the clinic and completed a CXR to rule out active TB.

Following a subsequent clinic visit, all eligible participants were cleared for 3HP treatment for LTBI and were administered a second informed consent, followed by a 60-minute questionnaire that assessed general health and psychosocial and behavioral variables. All participants were paid \$3 for the screening questionnaire and, if eligible, \$5 for further laboratory tests at the clinic and \$20 for the completion of baseline measures.

RN/CHW LTBI Program Training and Competency Evaluation

Upon development of the intervention protocol, the RN/CHW team was trained to deliver the 3HP LTBI intervention. The team was composed of a research RN and four part-time CHWs. CHWs were selected because they were formerly homeless adults who had transitioned out of homelessness, had excellent social skills, were positive role models, and had knowledge of the community and culture of homelessness. During the research team training, each member completed human subjects and Health Insurance Portability and accountability Act of 1996 (HIPAA) training, quizzes evaluating knowledge, baseline and follow-up questionnaire administration and mock training, and case studies of PEH with corresponding discussions. After the research leadership team introduced all content and knowledge that were assessed verbally using discussions, role play, and teach-back methods, the RN/CHW team was evaluated by the primary investigator and research investigators using a comprehensive competency checklist.

Development of RN/CHW 3HP LTBI Weekly Operations, Fidelity Monitoring, and Oversight

During the study implementation, a weekly operations and fidelity report on Research Electronic Data Capture was used to track outreach (e.g., flyer distribution, recruitment, information sessions, and screening), participant clinic appointments (e.g., laboratory tests, CXRs, and purified protein derivative test/CXR test result), physician clearance,

daily monitoring, weekly activities, and sessions. On a daily basis, the RN/CHW team reported to the research investigators and project coordinator. Every week, the research team went over the weekly operations, discussed, and evaluated research study progress. Based on these reports, concerns that arose during intervention implementation were addressed using constant evaluation and brainstorming, and creative approach to mitigating further challenges was discussed.

Intervention: RN/CHW Intervention Delivery

Each CHW was assigned seven to eight participants. At a mutually convenient time, the RN/CHW team met weekly with participants, under the direction of the RN, and assessed any side effects before the next dose. If none, the CHW provided directly observed treatment in a screened and private area. After the first dose of 3HP treatment, CHW conducted weekly one-on-one, 20-minute case management sessions over 12 weeks, where detailed information was provided about the program, along with coaching support to identify personal values and goals participants set for themselves. Education about TB and LTBI, its dangers, and the need for support to counteract the barriers of drug and alcohol use and mental health issues to 3HP medication completion was provided. Participants were encouraged to apply the problem-solving model to different hypothetical situations that served as triggers to engage in substance use and so forth. Progress was reviewed in overcoming barriers to medication adherence and appointment keeping.

The team also provided health and social service referrals (e.g., physical, mental health, substance treatment, and housing) and regularly tracked (detailed searching) participants who missed a 3HP dose. This tracking process was explained during the consenting process. If the participant failed to meet the team for the next dose, the team would begin making calls to reconnect based upon the locator information provided by the participant. This process occurred when a dose was missed on a specific date or a follow-up appointment was missed. Based on guidelines, participants who received 11 of 12 doses over 16 weeks were considered completers. Those who had a gap of >4 weeks between doses were noncompleters and were encouraged to restart the treatment.

Historical Control Group

In our comparison group, the historical control was provided the 3HP LTBI treatment to PEH attending a clinic. As a result of an outbreak in the Skid Row area of Los Angeles in 2014, the county investigated and screened 727 homeless adults. Over two thirds of the sample participants were between the ages of 35 and 54 years, whereas the remainder were 55 years and older. Three quarters of the sample participants were equally distributed as Black or Hispanic, whereas 13% were White and 2% were Asian. Among the 727 screened, 159 (21.8%) were LTBI positive, and 107 (67.3%) were recommended for 3HP treatment. Among the 56 who initiated treatment, 37 (66%) completed treatment.

Instruments

In this study, the primary dependent variable was completion of a 12-dose 3HP LTBI treatment compared to a historical, clinic-based control group that obtained 66% completion among homeless adults. Secondary outcome variables included an assessment of decline over time of the mental health symptoms of depression and anxiety and the drug use score and problematic alcohol use.

Independent Variables

Sociodemographic factors included age, gender, race/ethnicity, country of birth, and housing history (e.g., own/living with family or friends; shelter, street, living with family, friends).

General health was measured using five items from the general health perceptions subscale of the RAND 36-Item Short-Form Health Survey (SF-36; Ware & Sherbourne, 1992). Participants responded to five statements, such as “my health is excellent” or “I expect my health to get worse,” with response options ranging from “true” to “definitely false” and end points 100, 75, 50, 25, and 0, with several items reverse scored. A total score was determined by calculating the average, where higher scores of 80+ were termed as “more favorable,” scores of 60–80 were termed as “favorable,” and scores of <60 were termed as “less favorable” perception of health. For this measure, Cronbach’s $\alpha = .78$.

Social support was measured using the Medical Outcome Study Social Support Survey (Sherbourne & Stewart, 1991), a 19-item instrument that assesses availability of social support and includes four subscales: emotional/informational support (eight items, $\alpha = .95$), tangible support (four items, $\alpha = .94$), positive support (three items, $\alpha = .98$), and affectionate support (three items, $\alpha = .96$). Participants respond on a 5-point Likert scale, ranging from 1 (*none of the time*) to 5 (*all of the time*), with higher scores indicating more social support. We have thus labeled the scores as *high* (75+), *moderate* (25–74), and *low* (<25) social support. An overall support index was also calculated ($\alpha = .98$).

Primary Dependent Variables

3HP Treatment Completion

As further clarified in the data analysis section, treatment completion was calculated by totaling the number of doses completed by each individual, with completion defined as 11 of 12 doses. The percentage of treatment completion was calculated using 95% confidence intervals.

Secondary Outcome Variables

Drug use score and problematic alcohol use, as well as the mental health symptoms of depression and anxiety, were assessed to observe the effect on the primary outcome of treatment completion, as well as the decline over time, and constitute secondary

outcomes of this study. These variables were of critical importance as they are historically considered significant barriers to treatment completion.

Drug use score and problematic alcohol use were measured using the Texas Christian University (TCU) Drug Screen 5 (^{Institute of Behavioral Research, 2020}), a 17-item measure that screens for mild to severe substance use disorder per the Diagnostic and Statistical Manual for Mental Disorders (5th Edition). Participants indicated either “yes” or “no” responses to substance dependency questions and frequency of drug use based on a 5-point scale from 1 (*never*) to 5 (*daily*). The TCU Drug Screen 5 is scored on a point system, ranging from 0 to 11. Participant scores correspond to the number of symptoms endorsed by the participant and the severity of substance use disorder, including mild disorder (2–3 points), moderate disorder (4–5 points), or severe disorder (6 or more points). Problematic use of alcohol and specific drugs was defined as self-identified as being a problem (TCU Item 12) or daily consumption. For this measure, Cronbach’s $\alpha = .89$.

Depression was assessed using the Center for Epidemiological Studies Depression Scale–Revised, a 10-item measure used to screen for depression (^{Eaton et al., 2004}). This scale assesses depressive symptoms using a 4-point Likert scale that reflects the frequency of a symptom in the past week, ranging from 0 (*rarely or none of the time*) to 3 (*most of the time*). Example items include “I was bothered by things that do not usually bother me,” “I felt depressed,” and “I felt fearful.” Responses are summed (range: 0–30); a total score above 10 indicated depression. Reliability was good (Cronbach’s $\alpha = .79$).

Anxiety was measured using the Generalized Anxiety Disorder-7, a seven-item self-report instrument used to screen and assess for anxiety, using a 4-point Likert scale ranging from 0 (*not at all*) to 3 (*nearly every day*; ^{Spitzer et al., 2006}). Example items include “worrying too much about different things,” “trouble relaxing,” and “not being able to control worrying.” Scores were summed and ranged from 0 to 21. The severity of anxiety was determined with cutoff scores of 5 (*mild anxiety*), 10 (*moderate anxiety*), and 15 (*severe anxiety*). In this study, reliability was very good (Cronbach’s $\alpha = .87$).

Statistical Analysis

Descriptive statistics, including frequency and percentages, were computed for all variables. We assessed reliability of psychosocial scales used in our study by estimating Cronbach’s alpha. Our primary outcome was 3HP treatment completion, defined as completing 11 of 12 3HP doses. We estimated this outcome by dividing the number of participants with treatment completion by the total eligible participants and calculated the 95% confidence intervals using the scoring method. The lower bound of the 95% confidence limit was compared to 66% historical completion to assess successful improvement. We used mixed-effects models to account for within-participant correlation across time for the secondary outcomes of changes in drug use severity, anxiety, and depression scores.

For each model, the secondary outcome was specified as the dependent variable, time point as an ordinal independent variable, and subject identification as the random

variable. We also investigated the changes in problematic use of alcohol (binary outcome, yes vs. no) over time by fitting a generalized estimating equation to account for repeated measures over time for each subject. R v4.0.2 packages Hmisc, gee, and lme4 were used for analysis (R Core Team, 2020).

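### The primary endpoint's calculation rule omits the 16-week and >4-week-gap conditions that the intervention section uses to define completers

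*Combined protocol and SAP*

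**What the plan says.** Four places in the combined protocol and SAP describe completion.

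- **Intervention: RN/CHW Intervention Delivery.** Citing guidelines, it says that "participants who received 11 of 12 doses over 16 weeks were considered completers". It continues: "Those who had a gap of >4 weeks between doses were noncompleters and were encouraged to restart the treatment".
- **Instruments.** Here "the primary dependent variable was completion of a 12-dose 3HP LTBI treatment", compared with the clinic-based historical control.
- **3HP Treatment Completion** (under Primary Dependent Variables). It gives the calculation: "treatment completion was calculated by totaling the number of doses completed by each individual, with completion defined as 11 of 12 doses". For detail it points elsewhere: "As further clarified in the data analysis section".
- **Statistical Analysis.** The primary outcome is "3HP treatment completion, defined as completing 11 of 12 3HP doses". The rate is completers divided by total eligible participants, with a 95% interval by what the text calls the scoring method. The test is then: "The lower bound of the 95% confidence limit was compared to 66% historical completion to assess successful improvement".

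The benchmark comes from the Historical Control Group section: "Among the 56 who initiated treatment, 37 (66%) completed treatment". That section does not say how completion was defined there.

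**The concern.** All four places are built on the same course of doses, and three share the 11-of-12 threshold, but only the intervention section adds a time window and a gap rule. The section that states the calculation sends the reader to the Statistical Analysis, which adds neither condition and does not refer back to the intervention section. An analyst working from the analysis text alone would not apply them, and a reader cannot tell which classification lies behind a reported completion rate.

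The difference has a direction. Anyone who meets the intervention section's conditions has also reached 11 doses, so over a common denominator the dose-total rate is at least as high as the conditional rate. Any discrepancy pushes the lower confidence limit up, towards a declared improvement over 66%.

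Two further points are left open: whether doses before and after a restart are added together, and whether a completed restarted course makes a person a completer. The 12-dose wording in Instruments points to a single course; totalling by individual does not exclude pooling.

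**Working it through.** **1. The plan's own figure.** 37/56 = 0.6607, which reproduces the stated 66%. The documents give no analysed N, planned rate or power against which to check anything further.

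**2. Can the two rules classify the same person differently?** Assume that the 16 weeks run from the first dose (the start is not stated). Time to the 11th dose is the sum of 10 intervals. With nine weekly intervals and one gap of g weeks, it is 9 + g weeks.

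| Dosing pattern | Weeks to 11th dose | Dose total | Within 16 weeks | No gap >4 weeks |
|---|---|---|---|---|
| one gap of 5 weeks | 14 | completer | yes | no |
| one gap of 6 weeks | 15 | completer | yes | no |
| one gap of 7 weeks | 16 | completer | yes | no |
| one gap of 8 weeks (e.g. 5 doses, gap, 6 doses) | 17 | completer | no | no |
| ten 2-week intervals (off the weekly schedule) | 20 | completer | no | yes |

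So the rules can differ. The first three rows take the natural reading of the intervention section, that a long gap makes a noncompleter even when 11 doses fall inside the window; the sponsor should confirm it. If calendar weeks are numbered instead of elapsed time counted, the 7-week case has its 11th dose in week 17 and also fails the window.

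**3. How many reclassifications would change the conclusion?** I read the scoring method as the Wilson score interval without continuity correction, z = 1.96:

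lower limit = [p + z²/(2n) − z√(p(1−p)/n + z²/(4n²))] / (1 + z²/n)

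For 40/50: (0.8 + 0.0384)/1.0768 = 0.7786; half-width 1.96 × √(0.0032 + 0.000384)/1.0768 = 0.1090; lower limit 0.6696.

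N is assumed, except that 28 and 32 come from four CHWs (training section) times seven or eight participants each (intervention section): 4 × 7 = 28 and 4 × 8 = 32. Whether that is the whole sample or a concurrent caseload is not stated.

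| N | Fewest completers that pass | Lower limit | Lower limit with one fewer |
|---|---|---|---|
| 28 | 24 (85.7%) | 0.6851 | 0.6441 |
| 32 | 27 (84.4%) | 0.6825 | 0.6469 |
| 50 | 40 (80.0%) | 0.6696 | 0.6476 |
| 100 | 76 (76.0%) | 0.6677 | 0.6570 |
| 200 | 146 (73.0%) | 0.6646 | 0.6593 |

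Reclassifications that turn a pass into a fail = dose-total completers − fewest passing + 1.

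| Assumed dose-total rate | N | Calculation | Share of completers |
|---|---|---|---|
| 80% | 50 | 40 − 40 + 1 = 1 | 2.5% |
| 80% | 100 | 80 − 76 + 1 = 5 | 6.3% |
| 80% | 200 | 160 − 146 + 1 = 15 | 9.4% |
| 90% | 50 | 45 − 40 + 1 = 6 | 13.3% |
| 90% | 100 | 90 − 76 + 1 = 15 | 16.7% |
| 90% | 200 | 180 − 146 + 1 = 35 | 19.4% |
| about 90% | 28 | 25 − 24 + 1 = 2 | 8.0% |
| about 90% | 32 | 29 − 27 + 1 = 3 | 10.3% |

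At N = 28 or 32, a rate near 80% fails under either definition, so the choice would not alter the conclusion there.

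**The case against.** The best defence is that the intervention section gives the full definition once and the later sections abbreviate it. It uses the outcome's own vocabulary, completers and noncompleters, and nothing later contradicts it on time or gaps. That reading is possible, and the documents do not show that a dose-total rule was in fact applied. But no text supports the shorthand reading, and the 3HP Treatment Completion section describes a computation whose only cross-reference leads to a section without the conditions.

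A second objection is that people with long gaps were encouraged to restart. If they did, the gap patterns above reach 11 doses only by pooling two courses, which a single-course reading excludes. This narrows the problem but does not remove it: late finishers and anyone who resumed without restarting are still classified differently, and pooling is not ruled out.

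Third, the reclassification counts measure distance from a threshold under assumed N and rates, and would do so for any misclassification. The 1-of-40 case sits exactly on the minimum passing count. This is fair; the counts are illustrative and do not estimate how many people were affected.

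Finally, the unknown definition behind 37/56 is a separate comparability question that would remain if the trial's own sections agreed. That is also right; it matters here only because it leaves open which classification is like-for-like with the control.

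**Conclusion.** The concern holds and should be fixed. The calculation rule for the primary endpoint, as written, omits conditions that the plan states elsewhere, and any resulting discrepancy favours passing the 66% test. The direction rests only on a common denominator. Confidence is high that the sections disagree as written.

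Whether anyone was affected, and by how much, cannot be determined from the documents. Under the assumed sample sizes and rates, the reclassified share needed to reverse a pass runs from 2.5% to 19.4% of completers. Those figures depend on the Wilson reading of the interval. Which completion rule is clinically appropriate is not judged here; the passages must be reconciled.

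**What to change.** - Reconcile the intervention, Instruments, 3HP Treatment Completion and Statistical Analysis sections into one governing definition, and use it in the Statistical Analysis. The sponsor should state whether the time and gap conditions apply, from when the 16 weeks are counted, whether doses before and after a restart are pooled, and whether a completed restarted course counts.
- Report the completion rate and Wilson interval under both the dose-total and the intervention-section classification, and say whether the conclusion against 66% is the same.
- State how completion was defined for the 37 of 56 controls, or that it is unknown.

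The cost is wording in the endpoint and analysis sections plus one extra derivation. The derivation needs dose dates. Their availability is not stated, but directly observed dosing and the tracing of people after a missed dose date suggest that they were tracked. The downside is that the rate under the intervention-section conditions may be less favourable, and if the two classifications fall on different sides of 66% the conclusion would have to be qualified.

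### The success rule divides completers by eligible participants but tests the result against a benchmark computed only among people who started treatment

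*Combined protocol and SAP*

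**What the plan says.** Statistical Analysis defines the outcome: "Our primary outcome was 3HP treatment completion, defined as completing 11 of 12 3HP doses". The rate is obtained by "dividing the number of participants with treatment completion by the total eligible participants", and the plan "calculated the 95% confidence intervals using the scoring method". The decision rule follows: "The lower bound of the 95% confidence limit was compared to 66% historical completion to assess successful improvement".

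Recruitment, Informed Consent, and Compensation describes who is eligible: "all eligible participants were cleared for 3HP treatment for LTBI and were administered a second informed consent". That point comes after testing, chest X-ray and a further clinic visit, but before dose 1. The same section also uses the word for an earlier stage, when it ties payment for further laboratory tests to being eligible. No section says whether someone eligible who never takes a dose stays in the denominator.

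Historical Control Group gives the source of the benchmark. Of 727 people screened, 159 were LTBI positive, and of these "107 (67.3%) were recommended for 3HP treatment. Among the 56 who initiated treatment, 37 (66%) completed treatment".

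The secondary outcomes under Instruments are depression, anxiety, drug use and alcohol use. Starting treatment is not an outcome, and no section compares the trial's pre-treatment steps with the historical ones.

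**The concern.** A single-arm comparison with a fixed historical rate is interpretable only if both rates describe the same kind of person at the same step. Here the benchmark begins at the first dose, while the trial denominator, as written, begins at clearance and second consent. Nearly half of the historical patients recommended for treatment were lost between those two kinds of step, so the choice matters.

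Restricting the trial to starters would align the definition but not the route. Trial participants came through shelter outreach, escorted visits, a second consent and a paid 60-minute questionnaire. The historical group came through a clinic-based outbreak response whose steps before dose 1 are not described. Repeated attendance could remove people who would not keep weekly appointments; escorting and outreach could bring in people who would otherwise not start. Either would shift completion among starters without any change in adherence support.

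At stake is what a pass or a fail of the rule can be taken to mean.

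**Working it through.** **Inputs.** 159 LTBI positive, 107 recommended, 56 started, 37 completed (Historical Control Group); rule and interval method (Statistical Analysis). The scoring method is taken to be the two-sided Wilson score interval. The trial's sample size is not stated, so a range is used where it is needed.

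**Reproducing the plan's figures.** 37/56 = 66.1%, which matches 66%. 107/159 = 67.3%, which matches.

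**The historical cascade after recommendation.**
- Started: 56/107 = 52.3%
- Never started: (107 − 56)/107 = 51/107 = 47.7%
- Completed, per person recommended: 37/107 = 34.6%

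**Intervals.** The Wilson limits are [p + z²/2n ± z√(p(1−p)/n + z²/4n²)] / (1 + z²/n), with z = 1.96.
- 37/56: 53.0% to 77.1%
- 37/107: 26.2% to 44.0%

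**Reading A: eligible non-starters count as not completing.** With 107 eligible, the lower limit first exceeds 66% at 81 completers (81/107 = 75.7%, lower limit 66.8%); 80/107 gives 65.8% and fails. At least 75.7% of eligible people would therefore have to start, against 52.3% historically. If starting stays at 56 of 107 and every starter completes, the rate is 52.3%, below 66% before any interval is drawn. Against the matching benchmark of 34.6%, treated as fixed, 47/107 is enough (lower limit 34.9%).

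**Reading B: only starters count.** Selection can then move the result with no change in adherence. These are scenarios, not estimates for this trial.
- Take the historical 56 starters and remove would-be non-completers before dose 1. Removing 10 of the 19 gives 37/46 = 80.4%, lower limit 66.8%: pass, with the same 37 completers. Removing 9 gives 37/47, lower limit 65.1%: fail.
- Assume an imperfect filter that removes half of would-be non-completers and 10% of would-be completers. The rate among those left is 0.66×0.9 / (0.66×0.9 + 0.34×0.5) = 0.594/0.764 = 77.7%. The pass probability is 52% at N = 56, 71% at N = 100 and 95% at N = 200, while completers fall from 37 to 56×0.594 ≈ 33.
- A filter unrelated to adherence leaves the pass probability at 2.0% to 2.9% for N = 50 to 200.

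**The two rates answer different questions.** Suppose 96 of 107 start and 63 complete. Among starters this is 63/96 = 65.6% (lower limit 55.7%), no gain on 66%. Per person recommended it is 63/107 = 58.9%, against 34.6% historically. The single rule in the plan would report only a failure.

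**The case against.** The best defence is that completion among starters is a legitimate target. Intervention: RN/CHW Intervention Delivery starts the weekly case management sessions after the first dose, so asking whether people who start go on to finish is a fair test of adherence support. Giving no credit for starting more people limits the scope of the rule; it is not an error. That stands.

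Three stronger readings that a reader might infer do not stand.
- *The rule looks only at people who reach treatment.* The written denominator is eligible participants; only the benchmark is clearly restricted to starters. On the literal reading, dropping out between clearance and dose 1 counts against the trial. The ten removals above then stay in the denominator, giving 37/56 with a lower limit of 53.0%: fail.
- *The trial filtered harder than the clinic did.* No trial counts are given, and the historical benchmark had itself lost 47.7% before dose 1. The passing scenario is also fragile: removing 2 would-be completers along with the 10 non-completers gives 35/44, lower limit 65.5%, a fail.
- *A programme that starts more people is penalised.* At 75% completion, 42/56 fails (lower limit 62.3%), 60/80 fails (64.5%) and 84/112 passes (66.2%). Failure at 60/80 is largely a matter of sample size; at a fixed rate, more starters move the rule towards a pass.

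It is also fair to say that 37/107 is not a perfect match. Historical recommendation and trial clearance are not shown to be the same step, so some selection would remain.

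**Conclusion.** The concern holds as a mismatch between denominator and benchmark. The plan leaves open whether eligible non-starters count, and neither answer makes the comparison with 66% sound as it stands. If they count, the trial is held to a starters-only bar that it cannot clear at the historical starting rate (52.3% at best). If they do not, the definitions agree but the groups are selected differently, and the plan contains nothing that would show it.

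The direction of any bias is unknown: the documents do not support saying that the result was inflated or deflated. The Reading B figures assume a filter related to adherence and sample sizes that the documents do not give. The Reading A result needs only the historical counts and the literal denominator.

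This should be corrected because it can change what is concluded, but it does not invalidate an adherence comparison among starters that is labelled as such.

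**What to change.** In Statistical Analysis, state the denominator and pair each rate with its own benchmark, showing the interval for both sides:
- completion among those who took dose 1, against 37/56 (66.1%, CI 53.0% to 77.1%);
- completion among everyone cleared for 3HP, including those who decline the second consent or never start, against 37/107 (34.6%, CI 26.2% to 44.0%).

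Add one table of the trial's LTBI-positive, cleared, started and completed counts beside 159/107/56/37, with a note that cleared and recommended may not be the same step. If only the per-starter rate is higher, limit the conclusion to completion among those who started. Do not make agreement between the two comparisons a formal success condition: it is debatable, and it is empty if the lower limit already exceeds 66% among everyone cleared, since it then exceeds 34.6% as well.

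The cost is some wording, a little tabulation and a second, lower completion figure. The weekly report described under Development of RN/CHW 3HP LTBI Weekly Operations, Fidelity Monitoring, and Oversight covers "participant clinic appointments (e.g., laboratory tests, CXRs, and purified protein derivative test/CXR test result), physician clearance", and doses are totalled per person. The counts should come from those records where available; the plan does not promise that every step was tallied.

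### Does the GEE for problematic alcohol use need a fixed working correlation or a different model to avoid a false decline from drop-out?

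*Combined protocol and SAP*

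**What the plan says.** The Instruments section lists as secondary outcomes the "decline over time of the mental health symptoms of depression and anxiety and the drug use score and problematic alcohol use". The Statistical Analysis section uses mixed-effects models with a subject random effect for drug use severity, anxiety and depression. Alcohol, being binary, is handled differently: its change was examined "by fitting a generalized estimating equation to account for repeated measures over time for each subject". The only other detail is that the R package gee was among those used. Working correlation, weights, type of standard error and treatment of missed assessments are not given.

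Three other places bear on the point:

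- **Alcohol as a barrier.** Secondary Outcome Variables says of the four secondary measures: "These variables were of critical importance as they are historically considered significant barriers to treatment completion". The intervention section describes education on "the need for support to counteract the barriers of drug and alcohol use and mental health issues to 3HP medication completion". Both concern finishing treatment, not attending assessments.
- **Follow-up.** Staff were trained in "baseline and follow-up questionnaire administration and mock training", so at least one later assessment was intended. On tracing of participants, the intervention section says: "This process occurred when a dose was missed on a specific date or a follow-up appointment was missed".
- **Size.** No sample size is given. The training section says "The team was composed of a research RN and four part-time CHWs", and the intervention section says "Each CHW was assigned seven to eight participants".

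**The concern.** A GEE with an independence working correlation and no weights compares the prevalence among those seen at each time point. If people with problem use at one visit are less likely to be seen at the next, and status persists within a person, the later samples hold fewer problem users and prevalence appears to fall. A likelihood-based mixed model, as used for the other three secondary outcomes, tolerates loss that depends on earlier observed values if the model is right. An unweighted independence GEE does not.

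The drift would run toward the result the study hopes to see, and there is no comparison group for this outcome to expose it. Alcohol-related loss is plausible in this population, and the sentence in the plan permits the exposed fit. At stake is whether a reported decline in one secondary outcome reflects less drinking or only who stayed.

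**Working it through.** The plan gives no figure to reproduce: prevalence, correlation, loss, number of time points and cohort size are all unstated for this outcome. Every rate below is an assumption. The true change is set to zero.

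**1. Direction, baseline plus one follow-up.** Let p be baseline prevalence, ρ the within-person correlation, and r1 and r0 the follow-up response in baseline problem users and in others. Prevalence among responders is

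[p·r1·(p + ρ(1−p)) + (1−p)·r0·p(1−ρ)] / [p·r1 + (1−p)·r0].

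With p = 0.3, ρ = 0.5, r1 = 0.7 and r0 = 0.9:

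- numerator: 0.21 × 0.65 + 0.63 × 0.15 = 0.1365 + 0.0945 = 0.2310
- denominator: 0.21 + 0.63 = 0.84
- prevalence: 0.2310 / 0.84 = 27.5%
- odds ratio: (0.275/0.725) / (0.3/0.7) = 0.885

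With r1 = 0.8 the result is 28.8% (odds ratio 0.94). With r1 = 0.5 it is 24.6% (0.76). With r1 = r0, or with ρ = 0, there is no drift. So the claimed direction is right, given the conditions.

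**2. Range with a random-intercept model.** Prevalence is 30%. Loss per wave is 20%, 30% or 40% after a visit with problem use, against 10% otherwise. The random-intercept SD on the logit scale is 1.0 to 2.5. Large-sample odds ratios, last time point against baseline:

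| Time points | Independence | Exchangeable |
|---|---|---|
| Two | 0.98 to 0.84 | 0.98 to 1.00 |
| Three | 0.96 to 0.71 | 0.96 to 1.00 |

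The 0.71 needs three time points, SD 2.5 and 40% against 10% loss at each wave. It corresponds to a fall from 30.0% to 23.3%. The mild case (20% against 10%) gives 0.90 to 0.98. An exchangeable structure removes most of the drift.

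**3. What it does at a size the documents suggest.** Four community health workers with seven to eight participants each give 4 × 7 = 28 to 4 × 8 = 32, if caseloads were not refilled. Simulated false declines at 30 participants (one-sided 2.5%, robust standard errors, 2,000 trials per setting):

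- independence, differential and equal loss together: 2.1% to 6.1%
- equal loss alone: 2.0% to 3.0%
- worst setting (three time points, SD 2.5, 40% loss): independence 6.1%, exchangeable 4.8%
- same setting with 20% loss: 3.7% for both

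Simulation error near 5% is √(0.05 × 0.95/2000), about 0.5 points. A repeat with separate code gave 2.5% to 5.8% for independence and 2.0% to 5.0% for exchangeable. For scale, the median standard error of the log odds ratio at 30 participants with 40% against 10% loss was 0.50 to 0.61. The worst drift is ln(0.71) = −0.34, inside one standard error.

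**4. What a change of method would buy.**

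- *Random-intercept logistic model.* It removes the drift in step 2, partly because the data were generated that way. At 30 participants, up to 10% of fits under no change gave no usable standard error. A separate simulation took a true fall from 30% to 12% with equal 10% loss. GEE with independence detected it in 31% to 49% of trials and the mixed model in 5% to 27%, with 6% to 28% of mixed fits unusable and counted as non-detections. Those runs used purpose-written quadrature code rather than lme4, Wald tests only and 300 fits per setting, and they have not been repeated. The odds ratio also becomes subject-specific.
- *Inverse-probability weights.* In large samples (two time points, response 70% against 90%) they restore the odds ratio to 0.99, against about 0.98 for exchangeable. With about 30 people the model for being observed would itself be weakly estimated.
- *Loss tied to current, unseen drinking.* With two time points the independence odds ratio is r1/r0 = 0.7/0.9 = 0.78. With three time points and 40% against 10% loss, independence gives 0.56 to 0.63, exchangeable 0.64 to 0.67 and the mixed model 0.64 to 0.68. Most of the drift stays whichever of these models is used.

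**The case for a change.** The best case for a change is that a reader cannot tell whether the exposed or the protected fit was run, that the possible error favours the hoped-for finding, and that naming a structure costs almost nothing. Cohort size is also uncertain. If caseloads were refilled, the effect grows: at 60 participants (three time points, SD 2.5, 40% loss) false declines are 11.9% under independence and 5.2% under exchangeable. At 100 the ranges over the settings with differential loss are 3.2% to 16.6% and 1.6% to 4.3%.

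Much of this stands. The omission is real, the direction is right, and the consequence rises with sample size. What does not stand is the step to a defect in the plan. Harm needs an independence fit, missed assessments, and more misses among problem users, and the documents state none of these. Their remarks on alcohol concern treatment completion, and missed follow-up appointments set off active tracing, which limits loss although it is not a statistical remedy. No passage supports a cohort of 60 or 100. GEE is a legitimate choice for a binary outcome with a population-average question, and its exchangeable form already gives most of the protection available.

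**Conclusion.** No change follows. The Statistical Analysis section leaves the working correlation and the handling of missed assessments open for one secondary outcome, and an analyst can fill that gap sensibly within the stated method. An exchangeable structure holds the large-sample odds ratio at 0.96 to 1.00 when loss depends on earlier observed status. At about 30 participants, fixing it in advance would lower the false-decline rate by roughly one percentage point in the worst setting tried (6.1% to 4.8%) and by nothing in the milder one.

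Replacing GEE with a mixed logistic model would be a trade-off: less drift of one kind against a different target, unstable fits and probably lower power at this size. Weighting is debatable with so few people. Neither of the two models compared removes most of the drift if loss follows current unseen drinking. Numbers assessed at each time point by baseline alcohol status would help a reader, but that is a matter of reporting the results.

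The conclusion rests on assumed prevalence, correlation and loss rates and on a cohort near 30. In a much larger cohort, with strong loss tied to earlier alcohol use, the choice of structure would matter more. The primary completion analysis is unaffected in every case.
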